During the 13-month treatment period, patients will self-administer an inhaled study drug dose as needed when they experience OFF episodes; study medication may be used up to 5 times daily. Every day during the treatment period, patients will record the following information in the Inhaled Dosing Log: the number of times the inhaler was used and the number of capsules used for each inhalation treatment. For the 3 consecutive days prior to Screening Visit 2 (SV2), Treatment Visit 1 (TV1), Treatment Visit 2 (TV2), Treatment Visit 3 (TV3), and Treatment Visit 4 (TV4), Treatment Visit 5 (TV5), and Treatment Visit 6 (TV6) in the PD Diary, patients will record their time asleep and their waking time in different PD states: time OFF, time ON without dyskinesia, time ON with troublesome dyskinesia, and time ON with non-troublesome dyskinesia.

The treatment period has 6 in-clinic visits (TV1, TV2, TV3, TV4, TV5, and TV6). In-clinic efficacy measures include the occurrence and severity of dyskinesia following treatment in the clinic, the 39-Item Parkinson's Disease Questionnaire (PDQ-39), the Patient Health Questionnaire (PHQ-9), the Impact of Parkinson's OFF Episodes Patient Survey, the Patient Global Impression of Change (PGI-C) rating scale, the Schwab and England (S&E) Activities of Daily Living (ADL) score; and UPDRS Part 2 score. In-clinic and at-home efficacy and safety measures will be compared between treatment groups. Patient safety will be evaluated using adverse event (AE) reports, physical examination, vital signs (blood pressure [BP], heart rate [HR], and respiratory rate [RR]), clinical laboratory tests, 12-lead electrocardiograms (ECGs), spirometry, carbon monoxide diffusing capacity (DLco) maneuver, the UPDRS Part 4 (Questions 32-35 and 36-39) score, the Parkinson's Disease Impulsive-Compulsive Disorders Questionnaire (QUIP), the Epworth Sleepiness Scale, the Columbia-Suicide Severity Rating Scale (C-SSRS), the Amphetamine Withdrawal Questionnaire (AWQ), the Dopamine Dysregulation Syndrome - Patient and Caregiver Inventory (DDS-PC), and the self-administered MDS-UPDRS Parts 1B and 2 (Movement Disorder Society -UPDRS).

The design of this study, including evaluation of the temporal objective motor responses in-clinic following development of an 'induced' OFF episode after the first morning LD dose is in keeping with studies of other therapeutics that have been developed for treating PD motor fluctuations (Dewey 2001, Grosset 2011).

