For CVT-301-naïve patients and patients from study [CVT-301-009](#), spirometry will be assessed at the neurology sites for screening and TV1. The baseline DLco will be performed at dedicated pulmonary sites prior to TV1, and the pulmonary sites will be exclusively responsible for the conduct of spirometry and DLco after TV1 (within 2 weeks prior to the 3-, 6-, 9-, and 14-month visits, and 4 to 5 weeks following completion of Treatment Visit 6 [TV6]). For patients from [CVT-301-004](#), spirometry will be assessed at the neurology sites at TV1, and the pulmonary sites will be exclusively responsible for the conduct of spirometry and DLco after TV1 as described for the CVT-301-naïve patients.

For all patients, the treatment period will be approximately 13 months (56 ± 2 weeks) in duration. The maximum anticipated duration of this study for patients from the [CVT-301-004](#) study will be approximately 67 weeks, including the final spirometry and DLco assessment which takes place 4 to 5 weeks following the treatment period. The maximum anticipated duration of this study for CVT-301-naïve patients and [CVT-301-009](#) patients, including the screening period and final spirometry and DLco assessments, will be approximately 72 weeks.

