1. Medical marijuana has been prescribed to the patient prior to the date of informed consent. Patients who have not already been prescribed medical marijuana prior to beginning study participation may not begin medical marijuana use during their participation in the study.
2. Medical marijuana is not being used to treat any contraindicated condition as defined in the protocol (i.e., glaucoma, cancer, etc.).

Patients meet all other eligibility criteria (including spirometry).

Patients must agree not to use medical marijuana (smoking, ingestion or any other potential route of administration) on clinic days, before coming to the clinic or while in the clinic, until all procedures have been completed and they are discharged.

All patients in this study will take their standard PD medications during the study including on the morning of each in-clinic treatment visit. The timing of the administration of the usual morning dose of PD medications may be adjusted by the investigator to accommodate the

patient's and/or clinic's schedule. On designated in-clinic dosing days, if the patient converts to an ON state after the study drug has been administered, and all post-treatment study procedures have been performed, the patient will resume their standard schedule of PD medications.

At home, patients should maintain their usual schedule of standard oral PD medications, in addition to using the inhaled study drug for the treatment of OFF episodes. Patients should not take inhaled study drug within 45 minutes following their prior dose of standard oral PD medication. Patients should not use inhaled study drug for the treatment of early morning OFF. Otherwise, study drug may be used during the waking day for the treatment of OFF episodes that occur in between doses of the patients' standard oral PD medications. Patients should not take oral PRN PD medications to manage their OFF states throughout the treatment period.

Standard Prescribed Oral PD Medication Use for Prolonged OFF Episodes

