- Investigational drugs. Patients must not have taken any investigational drugs (including investigational formulations of marketed products) for at least 4 weeks or 5 half-lives (whichever is longer) prior to SV1 and must not use them for the duration of the study.
- Smoking. Current smokers are permitted to participate in the study provided that they meet other eligibility requirements (spirometry and concomitant respiratory illness). They must agree to and are able to abstain from smoking on the day of each in-clinic visit while in-clinic through completion of all assessments for that visit day (including screening visits and in-clinic treatment visits).
- Oral PRN PD medications during the treatment period. CVT-301-naïve patients and CVT-301-009 patients are permitted to take oral PRN PD medications during the screening period and during the study drug holiday. However, *oral PRN PD medications are not permitted during the treatment period while taking study medication.*

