Spirometry equipment will be provided to each study site to perform all spirometry assessments for CVT-301-naïve patients and [CVT-301-009](#) patients at SV1, SV2 (if necessary) and TV1 (all patients). All other spirometry assessments will be collected during the DLco and spirometry visits that take place at the pulmonary function lab. Spirometry data collected at pulmonary function labs will be reviewed immediately by a pulmonologist on site for safety signals and then sent to and reviewed by a central Pulmonary Function Testing reviewer (TechEd Consultants).

11.1.7. Carbon Monoxide Diffusing Capacity (diffusing capacity of the lungs for carbon monoxide-DLco)

Patients will undergo DLco assessments, which will be acquired in accordance with ATS criteria ([Miller et al., 2005](#)), at a dedicated pulmonary function facility after SV2 (and prior to TV1; 301-naïve patients and [CVT-301-009](#) patients), within 2 weeks prior to TV3, TV4, TV5, and TV6, and at 4 to 5 weeks after TV6, as described in the [Appendix 3](#) through [Appendix 10](#). These assessments should be performed while the patient is in the ON state (as reported by the patient to the pulmonary technician). Pulmonary function facility technicians will perform a slow vital capacity maneuver, followed by DLco, and then spirometry. The pulmonary facilities will use

their own equipment to perform all necessary pulmonary function testing relevant to DLco acquisition.

DLco and slow vital capacity maneuvers will be assessed and processed in accordance with ATS/ERS standards. Spirometry procedures will be conducted at the same visits in the same manner as those conducted at clinical sites in accordance with ATS criteria (see [Section 11.1.6](#)).

All DLco data collected at pulmonary function labs will be sent to and reviewed by a central Pulmonary Function Testing reviewer (TechEd Consultants).

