## Statistical Analysis Plan

- Categories of changes (<-50%, -50% -<-40%, -40% -<-30%, , -30% -<-20%, , -20% -<-10%, -10% -<-10%, 10% -<20% , 20% -<30% , 30% -<40% , 40% -<50%, >=50%) from baseline for FEV1, FEV, FEV1/FVC ratio and DLCO by visit. The summary for FEV1 will also be provided by smoker status.

The descriptive summaries will be repeated for the subset of assessments meeting the ATS quality criteria.

Another subset analysis will be performed by excluding the DLCO data from patients with a very high intra-individual variability. For the purpose of this analysis, all patients who have a co-efficient of variation (CV) value >7.5% for FEV1 will be excluded. The CV will be calculated for each patient as standard deviation divided by the mean.

In addition to the descriptive statistics, the changes in the FEV1, FEV1/FVC ratio, and DLCO values within each treatment group and differences between the treatment groups will be estimated with MMRM. The model will include the treatment group (CVT-301 DL1 or CVT-301 DL2), treatment/study group (patients who received inhaled CVT-301 in CVT-301-004 study, patients who received placebo in CVT-301-004 study and CVT 301 naïve patients), visit (visits at 1, 3, 6, 9, and 12 months), the stratification variables (Hoehn and Yahr stage and screening FEV1 and/or FEV1/FVC) and the interaction between the treatment group and visit as fixed factors. The baseline spirometry value will be included as a covariate. An unstructured covariance structure will be applied for MMRM. In case the model will not converge with the unstructured covariance structure, the heterogeneous compound symmetry (CSH) or the heterogeneous Toeplitz structure (TOEPH) will be used instead. If the unstructured covariance structure will be used, the denominator degrees of freedom will be computed using the Kenward-Roger method. In case of other covariance structures, the BETWITHIN option will be used for the denominator degrees of freedom. The least square (LS) mean, standard error, and LS mean difference for the changes from baseline within each treatment group and overall, and between the treatment group at each visit; along with the 95% confidence interval (CI) will be provided in a table. Treatment group difference will be assessed with a 2-sided alpha level of 0.05, unless specified otherwise.

The SAS code planned for the analysis is outlined below.

```
proc mixed data=&data;
class pdsevl fevlbl trta stdygrp avisit usubjid;

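### The same-day tobacco and marijuana rules do not reach the pulmonary-facility visits where all scheduled post-TV1 spirometry and all DLco are measured

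*Protocol*

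**What the plan says.** Protocol 9.4.2 permits current smokers if they agree to "abstain from smoking on the day of each in-clinic visit while in-clinic through completion of all assessments for that visit day", a scope spelled out as "including screening visits and in-clinic treatment visits". For patients already prescribed medical marijuana, the ban runs "on clinic days, before coming to the clinic or while in the clinic, until all procedures have been completed and they are discharged". The marijuana rule therefore covers the time before arrival; the tobacco rule, limited to time in the clinic, does not.

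Protocol 5.2 counts six in-clinic treatment visits, TV1 to TV6. Clinic spirometry is scheduled only at screening and TV1. After that, Protocol section 7 says "the pulmonary sites will be exclusively responsible for the conduct of spirometry and DLco after TV1", and Protocol 11.1.6 says "All other spirometry assessments will be collected during the DLco and spirometry visits that take place at the pulmonary function lab". Under Protocol 11.1.7 these are appointments at a dedicated facility: one between SV2 and TV1 (naive and CVT-301-009 patients), one within 2 weeks before each of TV3, TV4, TV5 and TV6, and one 4 to 5 weeks after TV6.

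The facility instructions in Protocol 10.1 deal with the ON state and the order of manoeuvres. The reminder-call list in 10.1.3.1 mentions neither smoking nor marijuana. On the analysis side, SAP 9.1 provides that "The summary for FEV1 will also be provided by smoker status". It plans no such breakdown for DLco, whose predicted value is adjusted for haemoglobin (SAP 6.2).

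**The concern.** By writing these rules, the sponsor has already judged same-day tobacco and marijuana use worth controlling. Followed to the letter, though, the rules leave a patient free to use either just before a facility test, and those tests supply the primary endpoint after TV1.

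This matters because the primary objective (SAP 3.1) is to characterise lung function over time within CVT-301-treated patients. Everyone is on active drug, so no concurrent untreated arm can absorb a change in test conditions. Two consequences are possible. One is added variability in FEV1, FVC and DLco. The other is a shift in mean FEV1 change for patients whose baseline was taken under a rule that does not apply at follow-up. Smoker status describes a habit and cannot show whether a given test followed recent use.

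**Working it through.** **Step 1. Where the tests are and where the rules apply** (Protocol 9.4.2, 11.1.6, 11.1.7 and Appendices 2 to 10).

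| Visit | Scheduled lung-function test | Tobacco rule | Marijuana rule |
|---|---|---|---|
| SV1 (SV2 if repeated) and TV1, clinic | Spirometry | Only while in clinic | Yes, including before arrival |
| TV2 to TV6, clinic | None | Only while in clinic | Yes, including before arrival |
| Facility, SV2 to TV1 (naive, 009) | DLco and spirometry | No | No |
| Facility, before TV3, TV4, TV5, TV6 | DLco and spirometry | No | No |
| Facility, 4 to 5 weeks after TV6 | DLco and spirometry | No | No |

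Facility appointments outside both rules:
- CVT-301-004 rollovers: 4 + 1 = 5.
- Naive and CVT-301-009 patients: 1 + 4 + 1 = 6.

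The count is of scheduled tests. Protocol section 7 allows unscheduled spirometry if tolerability problems arise.

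**Step 2. Whether the FEV1 baseline was taken under a different rule from follow-up.** This depends on the patient's origin.

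- *Former CVT-301-004 placebo.* Baseline is TV1 of this study (Protocol 12.3). The visit table in SAP section 8, which SAP section 9 applies to spirometry, does not use their CVT-301-004 visits. They have no facility test in this study before TV1, so baseline is a clinic value and follow-up is a facility value. This is the clearest case.
- *Naive, including the CVT-301-005 observational arm.* They have both a facility spirometry and a TV1 clinic spirometry before the first dose. SAP 4.1 and the section 8 table point to TV1. SAP 6.2 takes the last non-missing pre-dose value. SAP 9.1 defines an arrival baseline for neurology-site data only, while the MMRM tables are labelled as Pulmonary Function Facility data. The source is not settled.
- *Former CVT-301-009.* They have the same two pre-dose tests but are excluded from the spirometry MMRM (SAP 9.1).
- *Former CVT-301-004 active.* Baseline lies in CVT-301-004 (SAP 6.2), whose smoking rules are not in these documents.

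Where the baseline is a TV1 arrival value, marijuana is controlled before that test. Tobacco is not, because smoking before arrival is allowed. The difference between baseline and follow-up rules is therefore mainly about marijuana.

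**Step 3. Size.** The documents give no share of users, no acute effect and no FEV1 standard deviation, and the sample size has no formal calculation (SAP 3.5). There is no stated figure to reproduce. As an illustration:

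shift in mean FEV1 change = (share with recent use at follow-up − share with recent use at baseline) × acute effect

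Assume a net difference in share of 2% to 10% and an acute effect of 25 to 100 mL:
- low: 0.02 × 25 mL = 0.5 mL
- high: 0.10 × 100 mL = 10 mL

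A patient who uses before both tests contributes nothing. If the baseline is also a facility value, the same absence of a rule applies at both times and the expected shift is 0. The gap is the same for DL1 and DL2, so it should cancel in the dose comparison.

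**The case against.** A reader might infer that baseline FEV1 is protected from recent smoking and every follow-up is not. The documents do not support that. The tobacco rule binds only inside the clinic, so it does little for a test taken on arrival. Naive and CVT-301-009 patients have a pre-dose facility spirometry that is just as uncovered. For patients already on CVT-301 in CVT-301-004, protection cannot be confirmed.

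A reader might also infer a spurious on-treatment fall in DLco. Every DLco in this study is done at a facility with no abstention rule, so no change of rule within the study could create one. Noise is the most that can be claimed. Nor do the rules guard visits without endpoints: TV2 to TV6 carry OFF-to-ON resolution at 60 minutes, dyskinesia, UPDRS Parts 2 and 4, vital signs and ECG. They lack only scheduled lung-function tests.

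The plan also has partial safeguards. Facility spirometry is to follow the clinic manner and ATS criteria (Protocol 11.1.7). SAP 9.1 repeats summaries on tests meeting ATS quality criteria and plans analyses without patients whose FEV1 coefficient of variation exceeds 7.5%. Chronic respiratory disease within the last 5 years is an exclusion. The change tables have a central band of about 10% either side of zero, so a small acute effect would move only patients already near a boundary.

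These points limit the size and direction of any harm. They do not close the gap: none is an abstention rule, none records same-day use, and the variability exclusion drops patients without identifying affected tests.

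**Conclusion.** The gap in scope is established by the text. Both rules miss all five or six facility appointments, and recent use is unrecorded at the tests behind the primary endpoint. The expected effect is avoidable noise in FEV1, FVC and DLco. A shift in within-group FEV1 change is possible where baseline is a TV1 clinic value, most clearly in former CVT-301-004 placebo patients and mainly through marijuana.

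Its size cannot be derived from the documents. The 0.5 to 10 mL range rests wholly on the assumed shares and effects above and shows only how the shift would scale. Rows for smokers in the FEV1 tables could be affected more than the overall mean, but by an unknown amount. No baseline-to-follow-up difference in rules for DLco within this study, and no bias between dose levels, is expected. This is a worthwhile low-cost improvement and does not undermine the trial's conclusions.

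**What to change.** - **Protocol 9.4.2.** Extend the sponsor's existing tobacco and marijuana rules to the day of every pulmonary-facility visit, from before the test until it is complete. Align the tobacco wording with the marijuana wording so that time before arrival is also covered at clinic spirometry.
- **Data collection.** Record time of last tobacco use and last marijuana use at each lung-function test, at clinic and facility.
- **Reminders.** Mention the rule when the facility appointment is booked and again in the existing call one week before each visit. Booking matters because the test may precede that call.
- **SAP 9.1.** Flag tests done after same-day use and give a sensitivity summary of FEV1 and DLco. State which site's pre-dose value is the baseline for the MMRM on facility data. A DLco table by smoker status is optional, since it does not capture same-day use.

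The cost is wording in the protocol and facility instructions, one recorded item per test and one extra summary. The downside is a small burden on users and an occasional rescheduled test.

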10. STUDY PROCEDURES

The overall schedule of assessments is provided in [Appendix 1](#), and specific time and events schedules for the screening visits and in-clinic treatment visits are provided in [Appendix 2](#) through [Appendix 11](#). Unless otherwise specified, all assessments will be performed by the investigator or other assigned personnel.

10.1. Assessments by Visit

Assessments are to be performed as outlined in the following by-visit subsections. Study assessments are also outlined in the [Appendix 2](#) through [Appendix 11](#).

10.1.1. Screening Period

CVT-301-004 patients will not be required to undergo the screening visits and will undergo TV1 after a 1- to 14-day period (or longer if approved by the Sponsor) following TV4 of the CVT-301-004 study.

CVT-301-naïve patients (including CVT-301-005 observational arm patients) and patients from the CVT-301-009 study will undergo a screening period of up to 35 days before randomization. The screening period will consist of 2 scheduled clinic visits: SV1 and SV2. The screening period may be extended an additional 7 days if repeat screening assessments are required. At SV1, after patients have provided informed consent, they will be assessed for study eligibility in ON and OFF states. At SV2, any screening assessment performed at TV1 will be repeated if needed to verify or re-check results, and inhaler training will be performed.

Patients who do not develop an adequate OFF or ON period at SV1 will be invited to re-attend on a subsequent day, but will be withdrawn if further observation shows they are unable to turn OFF during a regularly scheduled study visit in accordance with the procedures. In addition, if a patient is unable to complete all assessments or training at the scheduled SV1, he/she may be rescheduled to repeat the visit, and/or to return to the clinic for additional training.

10.1.1.1. Screening Visit 1 for CVT-301-Naïve Patients and CVT-301-009 Patients (within 35 days prior to randomization)

Patients should be instructed to bring all of their medications with them to SV1. The following list is a suggested schedule for this visit, with assessments outlined in [Appendix 2](#). (Note: If a patient arrives at the clinic in an OFF state, assessments will be done in an OFF state first, then they will be repeated in an ON state after the patient has taken his/her standard dose of LD-containing medications and converted to an ON state.)

1. Give the patient an explanation of the purpose and nature of the study, and receive his/her voluntary written informed consent before any study procedures are performed.
2. Determine eligibility according to inclusion/exclusion criteria.
3. Record medical history (including smoking history), concurrent medical conditions, and PD history.
4. Confirm diagnosis of PD using Steps 1 and 2 of the UK Brain Bank criteria in the ON state. (Refer to [Section 11.3.1](#) and [Appendix 14](#).)
5. Use the modified Hoehn and Yahr scale to assess PD severity (in an ON state). (Refer to [Appendix 15](#).)
6. Record the estimated average number of hours of OFF time during the waking day (not including early morning OFF time) as reported by the patient. Eligible patients must have, by self-report, motor fluctuations with daily OFF time averaging at least 2 hours per day (not including early morning OFF time and which will require confirmation using the PD Diary over a period of 3 consecutive days).
7. Check and record all PD medications (including the number of times per day that LD-containing medications are administered and total daily LD dose) and other concomitant medications. Confirm that the patient is on stable dosages of PD medications (at least 2 weeks for the LD-containing medication, and 4 weeks for the other PD medications. Ensure that specified concomitant medications have been stabilized in accordance with protocol-defined criteria.
8. Perform the MMSE (in an ON state).
9. Perform a full physical examination.
10. Complete the Pulmonary Function Baseline Questionnaire.
11. Record a 12-lead ECG (after patient has been in a supine position for at least 5 minutes, as per [Section 11.1.3](#)).
12. Measure standard vital signs (BP, HR, and RR) and orthostatic vital signs (BP and HR). Standard vital signs should be taken after the patient has rested in a supine or semi-supine position for at least 5 minutes, and orthostatic vital signs should be taken after the patient has been standing for 2 minutes (see [Section 11.1.2](#) for suggested detailed procedures).
13. Perform spirometry to measure FEV1, FVC, and FEV1/FVC ratio to assess lung function (this must be performed with the patient in the ON state).
14. Perform UPDRS Parts 1, 2, 3 and 4 in an ON state.

15. Train patients on how to assess their ON and OFF states and how to record their waking ON/OFF status in a screening PD Diary (time OFF, time ON without dyskinesia, time ON with non-troublesome dyskinesia, time ON with troublesome dyskinesia, and time asleep).
16. Perform concordance testing with the patients (while in the ON and OFF states) for recognizing different ON/OFF states and recording them appropriately in the PD Diary. Patients will be tested for competence at self-rating and must be within 75% concordance with the ratings of the examiner (at least 3 out of 4 half-hour sessions over the course of 2 hours); if concordance is not reached, the observation period may be extended for an additional 2 hours to obtain agreement on at least 6 of 8 half-hour sessions. The same training and testing may be repeated at an unscheduled visit between SV1 and SV2 or at SV2. If patients return for an unscheduled visit between SV1 and SV2 for concordance training and testing, the visit must occur more than 3 days prior to SV2. If patients do not achieve 75% concordance by the end of SV2, they will be considered screen failures.
17. Take samples for clinical laboratory tests, including a serum pregnancy test for females of childbearing potential (see [Appendix 13](#) for a list of laboratory parameters assessed). Patients do not need to be in a fasted state at the time of the laboratory sample; however, fasted status will be documented (with fasting defined as at least 4 hours following the last meal or snack)
18. Introduce the inhaler and perform inhaler training using sham capsules with the CVT-301 inhaler while in the ON state.
19. Patients will remain in the clinic and further PD medications will be withheld until they turn into an OFF state.
20. Perform the assessments in the following suggested order while the patient is in an OFF state: spirometry, UPDRS Part 3, patient training on self-report of ON/OFF states, and inhaler training using sham capsules with the CVT-301 inhaler.
21. Distribute the PD Diary; train patients to record time OFF, time ON without dyskinesia, time ON with non-troublesome dyskinesia, time ON with troublesome dyskinesia, and time asleep for the 3 consecutive days prior to SV2.
22. Distribute the Screening ON/OFF Episodes Log; train patients to record the number of OFF episodes experienced by the patients during their waking day for the 3 consecutive days prior to SV2.
23. If needed, train caregivers on how to prepare inhalers for patients and how to complete the PD Diary and Screening ON/OFF Episodes Log (diaries will be completed based on the *patient report*).
24. Monitor for AEs throughout the visit.
25. Review with patients (and their caregivers) the planned schedule of events for the remaining study visits, and the responsibilities of self-administration of study drug and of recording information in the at-home diaries. Schedule the next visit.

26. Ask patients to bring the PD Diary, the Screening ON/OFF Episodes Log, and all of their PD medications with them at SV2, to take their usual morning medications prior to the visit, and to note the time when they took them.

The next visit will be scheduled. The site will call the patient approximately 4 days before SV2 to confirm the next study visit and to remind patients of the study procedures and the requirements noted in Item 26 in the above list.

10.1.1.2. Screening Visit 2 for CVT-301-Naïve Patients and CVT-301-009 Patients (at least 4 days after SV1)

The purpose of this visit is as follows: (a) to repeat any screening assessment performed at SV1 if needed to verify or re-check results for eligibility and safety, (b) to review the PD Diary and Screening ON/OFF Episodes Log to confirm eligibility (if these were not done correctly, the site may have to reschedule this visit) (c) to perform spirometry and vital signs, if needed to verify or re-check results, and (d) to re-train the patient on proper inhalation technique with the inhaler and on recording PD Diary and Screening ON/OFF Episodes Log information. For the 3 consecutive days prior to SV2, patients will complete the PD Diary and the Screening ON/OFF Episodes Log. Before arrival at the clinic for SV2, the patient will take all of their usual prescribed non-PD medications and PD medications, including LD-containing PD medications.

The following list is a suggested schedule for this visit:

1. Upon the patient's arrival to the clinic, reconfirm eligibility from SV1, including review of the PD Diary and the Screening ON/OFF Episodes Log. In the PD Diary, if <80% of the awake time is filled in for the 3-day period, the diary training and concordance testing must be repeated. The training and concordance testing will also be repeated if the patient has not reached 75% or greater concordance with the examiner at SV1 or at an unscheduled visit between SV1 and SV2.
2. Record any changes in the usual PD medication dose and regimen.
3. Review concomitant medications.
4. Perform inhaler re-training using sham capsules with the CVT-301 inhaler and IFU. If the patient has undergone inhaler training in both the ON and OFF states at SV1, it may be done in either state at this visit.
5. Patient training on assessment of the ON/OFF state will be repeated.
6. Distribute a new PD Diary and Screening ON/OFF Episodes Log, and instruct the patients to complete both of them for the 3 consecutive days prior to TV1.
7. If needed, the following assessments from SV1 may be completed or repeated: MMSE (in ON state); full physical examination; 12-lead ECG; standard vital signs (BP, HR, and RR) and orthostatic vital signs (BP and HR); spirometry (in ON and OFF states); UPDRS Parts 1, 2 and 4 (in an ON state); UPDRS Part 3 (in ON and OFF states); ON/OFF concordance testing (in ON and OFF states); and clinical laboratory test, including serum pregnancy test, if applicable (with documentation of fasting status).
8. Complete the C-SSRS, Epworth Sleepiness Scale, and QUIP (preferably in an ON state).
9. Monitor for AEs throughout the visit.

10. Schedule a DLco assessment to be performed at an outside pulmonary laboratory after SV2 and prior to TV1. The assessment should be performed while the patient is in an ON state (as reported by the patient to the pulmonary technician) at the pulmonary function facility. As part of the procedure, a slow vital capacity maneuver will be performed, followed by DLco, and then spirometry.

If a patient is unable to complete a screening assessment at SV2, an additional visit (repeat SV2) may be scheduled prior to eligibility determination and randomization. Any repeat assessments should be performed in the respective motor state as described for SV1. The site will contact patients by telephone 4 to 6 days prior to TV1 to confirm the DLco assessment has been done, to confirm the next study visit, and to remind patients of the study procedures required prior to the next scheduled study visit (including completion of the PD Diary and Screening ON/OFF Episodes Log). In addition, the site should remind the patients during the call that they must be symptom-free of any flu-like syndrome or other respiratory infection for at least 3 days prior to TV1 and that they should contact the site if an intervening illness occurs prior to TV1. If the patient has any of these symptoms within this time period, this visit will be rescheduled once these symptoms have been resolved for at least 3 days.

